**Study Protocol - Effects of Simethicone and the Multi-strain
Synbiotic Multilac Baby on Fecal Calprotectin in Colicky Babies**

Document Date: December 07, 2020

Cover page

Study Protocol - Effects of Simethicone and the Multi-strain Synbiotic Multilac Baby on Fecal Calprotectin in Colicky Babies

Document Date: December 07, 2020

1. General Information

Infantile colic or extensive crying is a major burden for newborns, their parents and healthcare providers [Landgren and Hallström, 2011]. In most of the cases infantile colic will disappear after the first three to five months of life [Sung, 2018]. Nevertheless, due to its stressful nature for parents, infant colic is among the leading causes to consult a health care professional during early infancy [Lucassen, 2010]. The parental burden associated with infantile colic finally results in enormous pressure on pediatricians to prescribe at least some kind of remedy. Diagnosis of infantile colic can be based on the Wessel's criteria, defined by crying and restlessness for more than three hours a day for more than three days per week for more than three weeks [Wessel et al., 1954]. Depending on diagnostic details, occurrence rates between 3 to 40% of all infants have been found [Lucassen et al. 2001, Helseth and Begnum, 2002].

2. Background Information

The etiology of infant colic remains unclear [Sarasu et al., 2018], with a variety of potential causes (gastrointestinal, hormonal, neurodevelopmental, and psychosocial) discussed. This has resulted in a broad range of therapeutic approaches aiming to address the problem [Lucassen, 2010, Mai et al, 2018].

Simethicone [Simethicone], a mixture of dimethicone and SiO₂, is a rather old product that, it is claimed, acts as a topical barrier for protecting the gut mucosa against irritants. It is not absorbed and is virtually non-toxic. While its use in diagnostic procedures is well-established, the therapeutic effects in a number of gastroenterological indications are contradictory [Meier and Streuwald, 2007]. In infantile colic, a number of smaller simethicone trials [Metcalf et al., 1994, Sethi and Sethi, 188, Danielsson and Hwang, 1985] have been published, but evidence did not reach the threshold of significance. Despite the absence of evidence for beneficial effects, simethicone is widely used for the treatment of infantile colic in some countries.

There is growing evidence that the gut microbiotas of colicky infants significantly differ from those of non-colicky babies [Savino et al., 2004, Savino et al., 2005, Savino et al., 2009]. In the gut microbiota of colicky babies a lower level of commensal bacteria like lactobacilli and bifidobacteria and higher numbers of proteobacteria have been found. Among these proteobacteria were Escherichia and Klebsiella bacteria [Savino et al., 2011], which are well known for their gas-producing properties, as well as the potential production of inflammatory lipopolysaccharides (LPS). In addition, it has been described that the gut microbiota of colicky infants exhibits a slower bacterial colonization, a reduced microbiota diversity and a lower microbiota stability [De Werth et al., 2013]. These findings have triggered a number of studies investigating the effect of supplementation of the gut microbiota of colicky

Study Protocol - Effects of Simethicone and the Multi-strain Synbiotic Multilac Baby on Fecal Calprotectin in Colicky Babies

Document Date: December 07, 2020

babies with products containing probiotic bacteria without a prebiotic component (probiotics), or with (synbiotics).

Although infantile colic is in most cases a self-limiting condition, pediatricians are writing a prescription for most of the affected infants. Results from surveys, performed among German and Polish pediatricians, revealed that in these two countries simethicone and pro-/synbiotics were the most frequently prescribed products for infantile colic [Sommermeyer et al., 2020]. In a recently published study it was found that the multi-strain synbiotic, Multilac Baby, antagonizes the in-vitro growth of the pathogenic bacteria *Escherichia coli* EPEC, *Shigella sonnei*, *Salmonella typhimurium*, *Klebsiella pneumoniae* and *Clostridioides difficile* [Piatek et al. 2020]. A clinical study evaluating effects of simethicone and Multilac Baby demonstrated that the synbiotic significantly improved the crying behavior of colicky babies when compared with the effects of simethicone [Piatek et al., 2020, accepted for publication in *Beneficial Microbes*].

Findings of a disturbed gut-microbiota in colicky babies have triggered interest in investigating gut-inflammation in these babies. An established marker for the level of gut inflammation marker is calprotectin [Stríz & Trebichavský, 2004]. Calprotectin is a 24 kDa dimer of calcium binding proteins S100A8 and S100A9 [Pthirana et al., 2018]. The complex accounts for up to 60% of the soluble protein content of the neutrophil cytosol. The complex is resistant to enzymatic degradation, and can be easily measured in feces. Inflammatory processes result in an influx of neutrophils into the bowel lumen [Walsham & Sherwood, 2016] Since calprotectin comprises as much as 60% of the soluble protein content of the cytosol of neutrophils, it can serve as a marker for the level of intestinal inflammation Measurement of fecal calprotectin has been shown to be strongly correlated with 111-indium-labelled leucocytes - considered the gold standard measurement of intestinal inflammation [Costa et al., 2003; Gisbert & McNicholl, 2009]. So far, there is only one study published which has characterized the effects of the probiotic *L. reuteri* on the level of fecal calprotectin in colicky babies [Savino et al., 2018]. Based on the findings of this study it was concluded that probiotics have the potential to improve gut-inflammation in babies with infantile colic.

3. Objectives/Purpose

The objective of the study is to compare the effects of simethicone and the multi-strain synbiotic Multilac Baby on calprotectin levels in colicky and non-colicky babies.

Study Protocol - Effects of Simethicone and the Multi-strain Synbiotic Multilac Baby on Fecal Calprotectin in Colicky Babies

Document Date: December 07, 2020

4. Study Design

In a first step, the crying behavior of newborns shall be assessed by employing a parental daily diary for three weeks. Diagnosis of infantile colic will be based on the Wessel criteria (Rule of Three) [Wessel et al., 1954]: extensive evening crying for at least three hours per day, during at least three days per week, during the last three weeks.

[figure not shown]
After the diagnosis has been performed (Day 1), calprotectin shall be determined in non-colicky babies (Arm 1, n=30-40) and colicky babies (Arms 2&3, each n=50-60). Based on the results from this steps it will be possible to determine if average calprotectin levels of colicky babies are different compared to those of non-colicky babies.

Colicky babies will then randomly assigned to a treatment with simethicone (Arm 2, n=50-60) and treatment with Multilac Baby (Arm 3, n=50-60). Treatment duration will be four weeks (until Day 28). Crying behavior will be assessed with a parental daily diary during the last three weeks before the end of treatment. At the end of the treatment (Day 28), calprotectin level in feces will be performed by using a point of care test (Buehlmann Quantum Blue Calprotectin).

**Study Protocol - Effects of Simethicone and the Multi-strain
Synbiotic Multilac Baby on Fecal Calprotectin in Colicky Babies**
Document Date: December 07, 2020

5. Selection and Exclusion of Subjects

Work stream

Inclusion criteria

The study is aiming to recruit babies aged 3 to 6 weeks of aged.

Exclusion criteria

- Organic causes for crying
- Previous treatment with antibiotics
- Previous treatment with probiotic
- Previous treatment with synbiotic

**Study Protocol - Effects of Simethicone and the Multi-strain
Synbiotic Multilac Baby on Fecal Calprotectin in Colicky Babies**
Document Date: December 07, 2020

6. Treatment of Subjects

Calculation

<https://www.sealedenvelope.com/power/binary-superiority/>

Settings

Significance level (alpha)	5%
Power (1-beta)	80%
Percentage 'success' in control group	50%
Percentage 'success' in experimental group	75%
Sample size required per group	55
Total sample size required	110

Randomization

A two-treatment equal allocation randomization scheme will be used. Product will be allocated to patient based on the randomization scheme by the pediatrician on entry into the study.

<https://www.sealedenvelope.com/simple-randomiser/v1/lists>

[figure not shown]
Settings

Treatment groups	Group A, Group B
Block sizes	2,4,6,8,10
List length	100

Study Protocol - Effects of Simethicone and the Multi-strain Synbiotic Multilac Baby on Fecal Calprotectin in Colicky Babies

Document Date: December 07, 2020

Randomization process

Study Protocol - Effects of Simethicone and the Multi-strain Synbiotic Multilac Baby on Fecal Calprotectin in Colicky Babies

Document Date: December 07, 2020

Control Group – Non-colicky Babies (Arm 1)

It is planned to include 30-40 babies to this arm to determine the calprotectin levels in non-colicky babies.

Simethicone (Arm 2)

Treatment for four weeks with simethicone (Espumisan[®], 100 mg/ml, Berlin-Chemie / Menarini Polska Sp z o.o., Warsaw, Poland). Simethicone administered 3-6 times per day with each treatment comprising 6 drops of the 100 mg/ml emulsion. It is planned to include 50-60 patients to this arm.

Multilac Baby (Arm 3)

Treated for four weeks with one stick pack of a multi-strain synbiotic (Multilac[®] Baby, Vivatrex GmbH, Aachen, Germany) per day. Each stick pack of Multilac[®] Baby contains a total of 10⁹ colony forming units (CFU) with equal CFU amounts of the following probiotic bacteria: L. acidophilus LA-14, L. casei R0215; L. paracasei Lpc-3; L. plantarum Lp-115; L. rhamnosus GG, L. salivarius Ls-33, B. lactis BI-04, B. bifidum R0071, B. longum R0175 and 1.43 g of the prebiotic fructooligosaccharides. It is planned to include 50-60 patients to this arm.

7. Assessment of Efficacy

Crying behavior

Crying behavior will be assessed by using a parental diary (24-hour Parental Daily Report). Primary outcome measures are (i) “crying days last 3 weeks” and (ii) “average of daily evening crying duration last 3 weeks” and (iii) change of fecal calprotectin level between (Day 1 and Day 28).

Gut calprotectin level

Calprotectin will be measured in feces samples taken before start of treatment (Day 1) and at the end of treatment (Day 28) with Simethicone and Multilac Baby.

8. Assessment of Safety

Safety will be assessed by using a parental diary (24-hour Parental Daily Report).

9. Adverse Events

Adverse Events will be reported by the standard procedure established to report adverse events of pharmaceutical products by physicians.

10. Discontinuation of the Study

The study will be discontinued in case of:

Study Protocol - Effects of Simethicone and the Multi-strain Synbiotic Multilac Baby on Fecal Calprotectin in Colicky Babies

Document Date: December 07, 2020

- occurrence of adverse events,
- failure to recruit patients.

11. Statistics

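### The randomisation list has 100 places, but the sample size in the same section is 110; stopping at 100 gives about 76% power, not 80%

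*Combined protocol and SAP*

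**What the plan says.** The Calculation part of Section 6 (Treatment of Subjects) gives "Sample size required per group 55" and "Total sample size required 110". Its settings are 5% significance, 80% power, and success rates of 50% in the control group and 75% in the experimental group.

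The Randomization part of the same section says "A two-treatment equal allocation randomization scheme will be used". It then gives the generator settings: two groups, block sizes 2, 4, 6, 8 and 10, and "List length 100".

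The planned arm sizes are ranges. Section 4 (Study Design) describes "colicky babies (Arms 2&3, each n=50-60" and repeats the range at the point of randomisation. Section 6 says for each of the two treatment arms: "It is planned to include 50-60 patients to this arm". That makes 100 to 120 randomised babies. Arm 1, the 30 to 40 non-colicky babies, is not randomised and takes no places on the list.

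**The concern.** One section gives two different sizes for the same randomised comparison. A site that used up the list, or stopped at 50 per arm, would have met its enrolment plan and still missed the number on which the stated power rests. A site that went on to 110 or 120 would run out of allocations and would have to extend the list during recruitment, by a procedure that the text does not describe. The paediatrician allocates product from this scheme at entry, so the list is a working document and should be complete from the start.

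**Working it through.** **Inputs.** Success rates of 0.50 and 0.75, alpha 0.05, power 0.80, 55 per group, list length 100 and 1:1 allocation, all from Section 6. Two-sided testing comes from Section 11. The arm range of 50 to 60 comes from Sections 4 and 6.

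**Step 1: reproduce the plan's figure.** Two proportions, normal approximation, unpooled variance:

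n = (z₀.₉₇₅ + z₀.₈₀)² × [p₁(1−p₁) + p₂(1−p₂)] / (p₁−p₂)²

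= (1.960 + 0.842)² × (0.25 + 0.1875) / 0.25² = 54.94 (unrounded z values), rounded up to 55 per group and 110 in total.

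The plan's figure is reproduced. The pooled-variance version gives 58, or 66 with a continuity correction, so the unpooled formula is the right one for the comparisons below.

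**Step 2: compare the list with the targets.**
- Required: 110 − 100 = 10 places short.
- Planned maximum: 2 × 60 = 120, and 120 − 100 = 20 places short.
- Planned minimum: 2 × 50 = 100, just covered.

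Completing a final block would not close the gap. All block sizes are even and at most 10, so the longest overrun starts at 98 and ends at 98 + 10 = 108, still below 110. The text does not say that a final block would be completed.

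**Step 3: power by arm size.** With the same formula, power = Φ(0.25 / √(0.4375/n) − 1.96):
- n = 50: Φ(2.673 − 1.960) = 76.2%
- n = 55: Φ(2.803 − 1.960) = 80.0%
- n = 60: Φ(2.928 − 1.960) = 83.3%

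**Step 4: check by exact enumeration.** Section 11 allows a chi-squared or a Fisher exact test for percentages. Summing over both binomial distributions gives:

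| Per arm | Plan's formula | Exact, chi-squared (uncorrected) | Exact, Fisher |
|---|---|---|---|
| 50 | 76.2% | 74.5% | 67.5% |
| 55 | 80.0% | 78.9% | 72.1% |
| 60 | 83.3% | 81.8% | 76.0% |
| Loss, 55 to 50 | 3.8 points | 4.4 points | 4.6 points |

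Only the last row measures the effect of the short list. The differences between columns come from the choice of test.

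**Step 5: the same loss as an effect size.** At 50 per arm and a control rate of 50%, the plan's formula needs an experimental rate of 76.0% instead of 75% to keep 80% power.

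**The case against.** The strongest reply is that a list length is a generator setting and not a stopping rule. Nothing in the text stops enrolment at 100, and the 50 to 60 range contains 55 and extends to 60, where the plan's formula gives 83.3%. That stands, and it makes the power loss conditional. It does not reconcile the numbers, because the list serves only the bottom of the range.

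The power figures also concern an undefined binary success. The primary outcomes in Section 7 are crying days, evening crying duration and "change of fecal calprotectin level between (Day 1 and Day 28". So 76% is not the power for any primary outcome. That stands too. But the 110 is the only sample-size justification in the protocol, and the list should agree with it.

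Some randomisation material could not be read: a figure beside the generator settings, the content under the Randomization process heading, and the Randomization Letter appendix. An extension may be described there, so whether one exists is unknown. The stated 100 would still conflict with the stated 110.

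Finally, the Fisher figures could make the problem look larger than it is. At 50 per arm the smallest expected cell is 50 × (1 − 0.625) = 18.75, so small counts give no reason to choose Fisher. That is fair, and the conclusion rests on the plan's own formula.

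**Conclusion.** The inconsistency is real and should be fixed, but its consequences are modest. The certain part is a list 10 places below the stated requirement and 20 below the planned maximum. The conditional part is a fall from 80.0% to 76.2% power if recruitment ends at the list length or at the lower arm size. This assumes the plan's rates of 50% and 75%, two-sided 5% testing and complete outcome data. The protocol gives no dropout allowance, so any missing outcomes would lower the power further. The shortfall does not bias the treatment comparison, and no threat to the integrity of allocation has been shown.

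**What to change.** Before the first baby is randomised:

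1. Generate the list at length 120 or more with the same block settings, so that it covers both the 110 and the planned maximum.
2. Give the randomised arm size as 55 to 60 in Sections 4 and 6, in line with the calculation. If 50 per arm is acceptable, keep the present range, restate the power as about 76%, and say that it applies to the binary success comparison and not to the three primary outcomes.

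The cost is a few minutes to regenerate the list and one wording change. Raising the lower limit to 55 lifts the permitted minimum from 100 to 110 babies, which is no more than the total that Section 6 already requires.
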